#### Sensitivity analyses of the primary endpoints for the effectiveness estimand

The sensitivity analyses will address the robustness of the primary approach for handling of missing values. In particular the sensitivity analyses address how assumptions on how body weight progresses after discontinuation of randomised treatment impact the estimated treatment difference between liraglutide 3.0 mg and placebo. The sensitivity analyses include the following.

- A multiple imputation approach as described by McEvoy where missing body weight measurement at week 56 for non-retrieved drop-outs (type MD) are imputed by sampling from values obtained from retrieved drop-outs (type AD) in each randomised treatment arm and according to the timing (monthly) of last available observation (of body weight) on randomised treatment (LAO-OT). Missing body weight measurements at week 56 for subjects on drug treatment (type MT) are imputed by sampling from type AT in the relevant randomised treatment arm. Thus, the imputation model for each randomised treatment arm and timing of LAO-OT is a linear regression of body weight (kg) at week 56 on the factors and covariates listed in Table 2–4 (except randomised treatment arm) with no interactions and LAO-OT of body weight. If timing by month is too restrictive, quarters, half-years, or excluding timing will be used.
- A weighted ANCOVA (wANCOVA) where returning drug discontinuing subjects (AD) are upweighted relative to their proportion of all drug discontinuing subjects (AD+MD) to account for the subjects not returning for assessments at week 56. Similarly, AT subjects are up-weighted relative to their proportion of all drug continuing subjects (AT+MT). The up-weighing is done by randomised treatment arm and the timing of LAO-OT. Subjects who are missing the weight measurement at week 56 (MD+MT) are assigned a weight of 0 (zero).
- A single imputation approach as done by Sacks. Missing weight measurement at week 56 for subjects who drop-out (type MD) are imputed using a weight regain rate of 0.3 kg/month after last available observation (LAO) of body weight. Change from baseline is truncated whenever the extrapolation would lead to a positive weight gain relative to baseline. LAO does not need to be the same as LAO-OT as subjects are allowed to come to scheduled visits after discontinuing randomised treatment. When a subject's LAO represents a gain in weight relative to baseline, no additional gain will be imputed, and the unfavourable gain is carried forward to week 56. Missing weight measurement at week 56 for subjects on treatment (type MT) will be imputed using the LAO. The weight regain imputation will be done for both randomised treatment arms.

Statistical Analysis Plan Trial ID: NN8022-4274 UTN: U1111-1177-5059 EudraCT No.: 2015-005592-24	CONFIDENTIAL	Date: Version: Status: Page:	07 July 2018 1.0 Final 14 of 24	Novo Nordisk
UTN: U1111-1177-5059 EudraCT No.: 2015-005592-24	CONFIDENTIAL	Status: Page:	Final 14 of 24	

Additionally, a version where only the liraglutide 3.0 mg arm uses the regain rate while the placebo arm uses LAO (corresponding to a weight regain rate of 0 kg/month) will be performed.

• Tipping point analysis. In a similar manner as above for a range of weight regain rates (starting from 0.1 kg/month and in intervals of 0.1 kg/month) for MD in liraglutide 3.0 mg arm will be used to define a tipping point in which superiority of liraglutide 3.0 mg disappears. In this analysis, the placebo arm will be imputed by LAO.

Figure 2–1 and Table 2–5 give an overview of the handling of missing values at week 56 assessments.

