## 2 Statistical considerations

Results from the statistical analysis will generally be accompanied by two-sided 95% confidence intervals and two-sided p-values.

Superiority will be claimed if the two-sided p-value is less than 5% and the estimated treatment difference/ratio favours liraglutide 3.0 mg.

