#### 2.1 Sample size calculation

The sample size calculation is based on the analysis approach addressing the primary estimand for the primary endpoints change in body weight (%) from baseline to week 56 (% weight change) and proportion of subjects losing  $\geq$  5% of baseline body weight at week 56 (5% responders).

The two primary endpoints will be tested in a hierarchical order.

The study design is a 1:1 randomisation with 282 subjects in total (141 subjects in each arm). Please see Table 2–2 for general specifications on sample size and power calculation.

 Table 2–2
 General specifications for sample size and power calculation

Endpoint	Statistical test	Minimum required power (%)
% weight change	Two-group Satterthwaite unpooled t test	90.0 (marginal)
	on the mean difference with $\alpha = 0.05$	
	assuming unequal variances	
5% responders	Pearson chi-square test for two	90.0 (marginal)
	independent proportions with $\alpha$ =0.05	

 $\boldsymbol{\alpha} {:} \text{ two-sided significance level}$ 

In the following paragraphs treatment differences and standard deviations (SD) are given without units.

Statistical Analysis Plan		Date:	07 July 2018	Novo Nordisk
Trial ID: NN8022-4274	CONFIDENTIAL	Version:	1.0	
UTN: U1111-1177-5059	CONFIDENTIAL	Status:	Final	
EudraCT No.: 2015-005592-24		Page:	9 of 24	

Body weight measurements from returning discontinuing subjects will be used in the primary analysis. But for the sample size calculations, it is assumed that all subjects who discontinue will not return at week 56 and that they have a % weight change like placebo subjects who completed the trial. It is expected that % weight change for liraglutide 3.0 mg subjects who discontinue might be somewhere in between completing placebo subjects and completing liraglutide 3.0 mg subjects. The assumption is thus expected to lead to a conservative effect estimate. In trial NN8022-1839 in non-diabetic subjects and with obesity, around 31% treatment discontinuations were observed in the placebo group, around 25% in the liraglutide 3.0 mg group. The calculated sample size ensures adequate power if the proportion of discontinuing subjects should be as high as 30%.

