Based on findings from NN8022-1839, a difference in % weight change between liraglutide 3.0 mg and placebo of -5 (-9% vs. -4%, SD=7) is assumed among completing subjects. For sample size calculation, a common SD of 7 was assumed for completers of liraglutide 3.0 mg or placebo. In NN8022-1839, a SD of 6.65 was seen for % weight change among subjects completing liraglutide 3.0 mg at week 56; 5.88 was observed among subjects completing placebo. Adjusting for 30% discontinuation and using a mixture distribution, a difference of -3.5 is expected in the primary analysis. A sample size of 282 subjects (141 in each arm), gives a marginal power of 98.3%.

For the primary endpoint 5% responders, the expected proportions were calculated based on the same assumptions as above. Adjusting for 30% discontinuation gives an expected 5% responders proportion of 63% in the liraglutide 3.0 mg arm and 44% in the placebo arm. With 282 subjects, this results in a marginal power of 90%.

Given these assumptions, the sample size of 282 subjects (141 in each arm), results in a combined power of 88.5%.

The tests of superiority of liraglutide 3.0 mg to placebo for each of the confirmatory endpoints are performed hierarchically in the order in which the endpoints are presented (see Sections 4.2.1 and 4.2.2.1 in the protocol). The two primary endpoints are included in the statistical testing hierarchy, and the primary objective will be met if superiority of liraglutide 3.0 mg vs. placebo is demonstrated for each of the primary endpoints. The test hierarchy is given in Table 2–3 with underlying assumptions, marginal power and effective power. The effective was calculated using a naïve and conservative approach, which assumes no correlation of endpoints by multiplying the respective marginal powers. Assumptions made to calculate the power for the two primary endpoints and all confirmatory secondary endpoints are also presented in Table 2–3.

Statistical Analysis Plan		Date:	07 July 2018	Novo Nordisk
Trial ID: NN8022-4274	CONFIDENTIAL	Version:	1.0	
UTN: U1111-1177-5059	CONFIDENTIAL	Status:	Final	
EudraCT No.: 2015-005592-24		Page:	10 of 24	

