### Figure 2–1 Illustration of imputation approaches for the effectiveness estimand

Jump to refere	nce (multiple imputation)
Liraglutide	AT+AD 7 MT+MD
Placebo	AT+AD MT+MD
McEvoy (multip	ole imputation)
Liraglutide	$ \begin{array}{c} AT \\ AD \end{array} \longrightarrow \begin{array}{c} MT \\ MD \end{array} $
Placebo	$ \begin{array}{c} AT \\ \hline AD \end{array} \longrightarrow \begin{array}{c} MT \\ \hline MD \end{array} $
McEvoy is done by	timing (e.g. monthly) of randomised treatment discontinuation
Sacks (single in	iputation)
Liraglutide	ATLAO $\rightarrow$ MTADLAO + 0.3 $\rightarrow$ MD
Placebo	$ \begin{array}{ c c c c c c c c c c c c c c c c c c c$
LAO: Last available	observation irrespective of whether on randomised treatment or not
An arrow indicates $AT = A$ MT = M AD = A MD = M	from which group an imputation is done vailable on randomised treatment lissing on randomised treatment vailable drop-out lissing drop-out

Statistical Analysis Plan Trial ID: NN8022-4274 UTN: U1111-1177-5059 EvdreCT No.: 2015 005502 24	CONFIDENTIAL	Date: Version: Status:	07 July 2018 1.0 Final	Novo Nordisk
EudraCT No.: 2015-005592-24		Page:	16 of 24	

Approach	Description	Assumptions
Jump to reference (multiple imputation)	Liraglutide and placebo MT+MD imputed from placebo AT+AD (i.e., all available placebo assessments at week 56)	
 
Liraglutide MD lose any treatment effect instantly after drop-out
 
Placebo AT and placebo AD are assumed to have the same weight loss
 

McEvoy (multiple imputation)	Separately for the two randomised treatment arms: MD imputed from AD by matching on time (month) of drop-out MT imputed from AT	
 
AD is representative of the MD for each randomised treatment arm
 
AT is representative of the MT for each randomised treatment arm
 

Weighted ANCOVA (wANCOVA)	No imputation. Separately for the two randomised treatment arms: AD subjects are up-weighted relative to their proportion of AD+MD and timing of drop- out AT subjects are up-weighted relative to their proportion of AT+MT	
 
AD is representative of the MD for each randomised treatment arm
 
AT is representative of the MT for each randomised treatment arm
 

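### In the retrieved-drop-out imputation, the regression for on-treatment subjects has its own outcome as a predictor, so missing on-treatment weights are carried forward; the weighted-ANCOVA text and Table 2–5 also disagree on timing

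*SAP*

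**What the plan says.** The text is in SAP Section 2.3.2.2, under the sensitivity analyses for the effectiveness estimand. Protocol Section 17.3.2.2 and Table 17–5 say the same.

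- **Definitions.** In SAP Table 2–1 an AT subject is on drug at week 56 with the assessment available, including subjects who stopped and restarted. MT is the same with the assessment missing. AD and MD are drop-outs with and without a week-56 value. LAO-OT is the last body weight available while on randomised treatment, with no condition that it precede week 56.
- **Retrieved-drop-out imputation.** MD values come from AD in the same arm, by monthly timing of LAO-OT. For the others, "subjects on drug treatment (type MT) are imputed by sampling from type AT in the relevant randomised treatment arm". One model statement follows both rules, for each arm and LAO-OT timing: week-56 weight on the Table 2–4 terms ("except randomised treatment arm) with no interactions and LAO-OT of body weight"). If months are too fine, quarters, half-years or no timing may be used.
- **Weighted ANCOVA.** AD are weighted up to AD+MD, AT up to AT+MT, and subjects with missing values get weight zero. Then: "The up-weighing is done by randomised treatment arm and the timing of LAO-OT".
- **Table 2–5 and Figure 2–1.** The table attaches timing only to drop-outs. For the rest, "AT subjects are up-weighted relative to their proportion of AT+MT". It gives as the assumption that AT represents MT in each arm. A note in the figure ties the timing in the imputation to discontinuation of treatment.

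**The concern.** An AT subject has a weight at week 56 and is on drug at that visit. By the SAP's definition, that weight is the subject's LAO-OT. The model for MT would therefore be estimated from subjects whose predictor and outcome are the same number.

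If the text is programmed as it stands, the analysis does not apply its stated assumption that AT is representative of MT. It also gives MT subjects the same value as the weight-regain single imputation and the tipping-point analysis, both of which already use the last available observation for MT. These analyses would then differ only in how they treat drop-outs, and the check offers no separate view of missing on-treatment data.

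Table 2–6 lists this imputation for both primary endpoints and for every confirmatory secondary endpoint except the week-16 responders. The weighted ANCOVA is listed for % weight change and the continuous confirmatory endpoints, not for the responder endpoints.

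**Working it through.** **1. The scale in the plan.** SAP Section 2.1 states that "a difference in % weight change between liraglutide 3.0 mg and placebo of -5 (-9% vs. -4%, SD=7) is assumed among completing subjects". With 30% discontinuing, the expected liraglutide mean is 0.7 × (−9) + 0.3 × (−4) = −7.5, so the difference is −7.5 − (−4) = −3.5, as stated: "Adjusting for 30% discontinuation and using a mixture distribution, a difference of -3.5 is expected in the primary analysis". The mixture SD is √(49 + 0.7 × 0.3 × 5²) = √54.25 = 7.37. With 141 per arm, a placebo SD of 7 and the unequal-variance t test, power is 98.3%, which agrees with the SAP. The point does not depend on this figure; −3.5 serves only as the yardstick.

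**2. The AT regression.** Let Y be week-56 weight and L be LAO-OT. The model is Y = b0 + b1·sex + b2·BMI class + b3·baseline weight + b4·L + e. For every AT subject L = Y. The residual sum of squares is zero at b4 = 1 with all other coefficients 0, so the residual variance is 0 and the posterior collapses to a point. An MT subject with last on-treatment weight L* is given Y* = L* in every copy.

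**3. Numerical check.** A simulated arm with 95 AT and 5 MT (assumed), 100 copies:

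| AT predictor | LAO-OT coefficient | Residual SD (kg) | Between-imputation SD for MT (kg) |
|---|---|---|---|
| LAO-OT as defined (week-56 weight) | 1.000 | about 10⁻¹² | 0 |
| Last on-treatment weight before week 56 | 0.92 | 1.50 | 1.3 to 1.5 |

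The second row assumes an SD of 1.8 kg for the change up to week 56. The first row is algebraic and needs no such assumption.

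**4. Timing cells in the imputation.** AT subjects have LAO-OT timing at week 56; MT subjects have it earlier. In a monthly cell that holds MT subjects but no AT subjects, no model can be fitted. With quarters, half-years or no timing, AT donors can appear, and step 2 then applies. For a given MT subject these outcomes are alternatives. Dropping timing cures the empty cell but not the self-regression.

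**5. Weights in the weighted ANCOVA.** About 0.70 × 141 = 99 subjects per arm continue. The text with monthly timing gives an AT weight of AT/AT = 1, because the week-56 cell holds no MT subjects. Table 2–5 gives (AT+MT)/AT. The split between AT and MT is assumed:

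| AT / MT | Weight, text | Weight, Table 2–5 | Continuing subjects represented, text / table |
|---|---|---|---|
| 97 / 2 | 1 | 99/97 = 1.021 | 97 / 99 |
| 95 / 4 | 1 | 99/95 = 1.042 | 95 / 99 |
| 89 / 10 | 1 | 99/89 = 1.112 | 89 / 99 |

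For illustration, suppose the 42 drop-outs in the liraglutide arm are fully represented and average −4, against −9 for continuers (the SAP's sample-size assumption). For 95/4, the continuers' share is 95/137 = 0.693 under the text and 99/141 = 0.702 under the table, so the unadjusted arm mean differs by (0.7021 − 0.6934) × 5 = 0.04 points. The same sum gives 0.02 for 97/2 and 0.11 for 89/10.

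**6. Size for the imputation.** The shift in an arm mean is the MT share times the mean change from the last observation to week 56. The documents give neither. With shares of 1% to 10% and changes of 0.2 to 1.0 percentage points, the range is 0.01 × 0.2 = 0.002 to 0.10 × 1.0 = 0.10 points.

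**The case against.** The strongest reply is that the intention is clear. A programmer would use the last weight before week 56. Figure 2–1 and Table 2–5 tie timing to discontinuation or drop-out, which AT and MT subjects have not had. Coarser timing is allowed. Carrying forward for MT is a deliberate choice elsewhere in the SAP. The effect is small, and the stated focus of these analyses is weight after discontinuation.

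Much of this stands. The figure and table show that timing was meant for drop-outs, so that part is a matter of aligning one sentence of text. Coarser timing can supply donors, although the allowance is written for the imputation and not for the weighted ANCOVA. Carrying forward is not wrong in itself. The small size also stands.

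It does not answer the predictor. Neither the table nor the figure defines it, and no separate model is given for MT. The unstated repair is also incomplete. Counselling visits are monthly after month 6 (protocol Section 3.1), so an AT subject's previous weight may be about a month old, while an MT subject's last weight may be much older. A slope learned over a short gap would be applied to a long one.

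A reader might infer that the weighted ANCOVA is degenerate too. It is not: LAO-OT weight is not a covariate there, and only its timing enters, through the weights.

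**Conclusion.** The point holds for the imputation model. As defined, LAO-OT for AT subjects is the outcome, so MT values are carried forward with no imputation variance, contrary to the stated sampling and to the assumption in Table 2–5. This follows from the definitions alone. It is certain for endpoints derived from body weight. For waist circumference, the two physical-function scores and walking distance, it arises only if LAO-OT is taken as that endpoint's own last value, which the SAP does not specify.

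The weighted-ANCOVA point is a conflict between text and table that changes the weights, and it arises only if the text's timing rule is applied to AT and MT.

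A reader might infer that the primary result is in doubt or that on-treatment missing data are mishandled throughout. The documents do not support that. Jump to reference uses no intermediate weights, and MD-from-AD is unaffected because an AD subject's LAO-OT precedes week 56. The imputation effect is 0.002 to 0.10 points on an arm mean, at most 0.10/3.5 = 3% of the expected difference, under the assumed MT shares and changes. The correction is still worth making, because the model cannot work as described.

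**What to change.** - **Imputation.** State that the MT-from-AT model uses, as the AT predictor, an on-treatment weight from before week 56, preferably at the visit that matches the MT subject's last on-treatment weight.
- **Timing.** State in both the imputation and the weighted-ANCOVA text that timing strata apply only to AD and MD, with AT up-weighted by (AT+MT)/AT within arm, as in Table 2–5.
- **Other endpoints.** Where these analyses are reused for endpoints other than body weight, say which last on-treatment value is the predictor.

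The first two items cost about two sentences in the SAP and the third a clause. No new data are needed, and the primary analysis does not change.

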#### Additional sensitivity analyses

Additional analyses will investigate how sensitive the primary statistical models (for primary endpoints) are to the choice of factors and covariates in the model as follows: A model resembling the primary analysis models using the same imputation method (jump to reference) adjusting only for baseline body weight and randomised treatment arm. The imputation model (step 1) will be same as for the primary approach.

For the binary primary endpoint, the risk difference (unadjusted for any factors and covariates) and corresponding 95% CI will also be calculated.

#### 2.3.3 Analysis method addressing the efficacy estimand for the primary endpoints

The efficacy estimand for % weight change will be assessed using a mixed model for repeated measurements (MMRM). The MMRM will use assessments only from subjects who are taking the randomised treatment until end of trial or at first discontinuing of trial drug (either temporarily or permanently). A pause of less than eight consecutive days is not regarded as discontinuation for this analysis. This means that assessments at week 56 for retrieved drop-outs (type AD) will be discarded. The MMRM will be fitted using % weight change and the same factors and covariates (Table 2–4) as for the primary analyses all nested within visit. An unstructured covariance matrix for measurements within the same subject will be employed, assuming that measurements for different subjects are independent.

The efficacy estimand for 5% responders will be assessed using the same MMRM. From the MMRM individually predicted values for % weight change at week 56 will be used to classify each subject as 5% responder or not. This classification will then be analysed using a logistic regression model with treatment as the only factor.

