17.3.3 Analysis method addressing the efficacy estimand for the primary endpoints

The efficacy estimand for % weight change will be assessed using a mixed model for repeated measurements (MMRM). The MMRM will use assessments only from subjects who are taking the randomised treatment until end of trial or at first discontinuing of trial drug (either temporarily or permanently). A pause of less than three consecutive days is not regarded as discontinuation for this analysis. This means that assessments at week 56 for retrieved drop-outs (type AD) will be

discarded. The MMRM will be fitted using % weight change and the same factors and covariates ([Table 17-4](#)) as for the primary analyses all nested within visit. An unstructured covariance matrix for measurements within the same subject will be employed, assuming that measurements for different subjects are independent.

The efficacy estimand for 5% responders will be assessed using the same MMRM. From the MMRM individually predicted values for % weight change at week 56 will be used to classify each subject as 5% responder or not. This classification will then be analysed using a logistic regression model with treatment as the only factor.

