#### Efficacy estimand

A secondary efficacy estimand (*de jure*) is quantifying the average treatment effect of liraglutide 3.0 mg relative to placebo 56 weeks after randomisation, as adjunct to reduced caloric diet, increased physical activity and CMS-IBT, if all randomised subjects had adhered to assigned treatment regimen for the entire duration of the trial.

#### Effectiveness estimand at week 16

In addition, an effectiveness estimand (*de facto*) is quantifying the average treatment effect of liraglutide 3.0 mg relative to placebo 16 weeks after randomisation, as adjunct to reduced caloric diet, increased physical activity and CMS-IBT, in all randomised subjects regardless of adherence to treatment.

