#### Primary approach for handling of missing values

The primary approach for multiple imputations of missing values of body weight at week 56 (type MT+MD) for both the liraglutide 3.0 mg and placebo group is by sampling among all available assessments at week 56 in the placebo group (type AT+AD). This approach is also known as jump to reference and makes the assumption that subjects instantly after discontinuation lose any effect of randomised treatment beyond what can be expected from placebo treatment as adjunct to diet and exercise. Body weight measurements at visits between baseline and week 56 are not used for this imputation approach. The multiple imputation approach is done in three steps.

- **Imputation**: Step 1 defines an imputation model based on placebo subjects, which is used to impute missing body weight values at week 56 in both arms. This will be done 100 times and results in 100 complete data sets. A more detailed explanation of this step is given below.
- Analysis: Step 2 analyses each of the 100 complete data sets, using the statistical model defined in Section 2.3.1.1 and 2.3.1.2 and saves the 100 estimation results.

• **Pooling**: Step 3 integrates the 100 estimation results into a final result using Rubin's formula. The imputation model in step 1, uses placebo subjects from FAS with non-missing body weight measurements at baseline and week 56. The imputation model is a linear regression of body weight

Statistical Analysis Plan Trial ID: NN8022-4274 UTN: U1111-1177-5059 EudraCT No.: 2015-005592-24	CONFIDENTIAL	Date: Version: Status: Page:	07 July 2018 1.0 Final 13 of 24	Novo Nordisk
---	--------------	---------------------------------------	--	--------------

(kg) at week 56 on the factors and covariates listed in Table 2–4 (except randomised treatment) with no interactions. The estimated posterior distribution for the parameters (regression coefficients and variances) in the imputation model is then used to impute missing week 56 body weight values for both randomised treatment arms.

If 100 copies are not sufficient to establish stable results, a higher number will be used. The multiple imputations will be generated using Novo Nordisk trial number 80224274 as seed number.

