#### 2.4 Secondary endpoints

#### 2.4.1 Confirmatory secondary endpoints

Confirmatory secondary endpoints are listed in Section 4.2.2.1 in the protocol.

All confirmatory secondary endpoints, except proportion of subjects losing at least 4% of baseline body weight at week 16, are planned to be assessed at week 56 and will be analysed using the same primary MI approach as used for the primary endpoints and to address the effectiveness estimand. The statistical model for continuous confirmatory secondary endpoints will be ANCOVA with covariates listed in Table 2–4 with baseline body weight replaced by baseline measurement of endpoint to be analysed. Binary confirmatory secondary endpoints will be analysed using logistic regression in the same way as for 5% responders.

The effectiveness estimand at week 16 will be assessed using the confirmatory secondary endpoint of proportion of subjects losing at least 4% of baseline body weight at week 16. Subjects with missing values for weight at week 16 will be considered non-responders.

Sensitivity analyses will be carried out for all confirmatory secondary endpoints, except for proportion of subjects losing at least 4% of baseline body weight at week 16. See Table 2–6 for details on planned analysis methods, multiple imputation approach and sensitivity analyses.

The efficacy estimand will also be assessed for confirmatory secondary endpoints, except for proportion of subjects losing at least 4% of baseline body weight at week 16, using MMRM as described for the primary endpoints.

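### Efficacy-estimand responders are classified from MMRM predicted week-56 values and analysed as observed, which biases responder rates and odds ratios and understates their standard errors

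*SAP*

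**What the plan says.** The efficacy estimand is secondary and hypothetical. It asks what the effect would be "if all randomised subjects had adhered to assigned treatment regimen for the entire duration of the trial" (SAP section 2, Efficacy estimand). SAP 2.3.3 fits an MMRM to on-treatment data only: "An unstructured covariance matrix for measurements within the same subject will be employed", and "assessments at week 56 for retrieved drop-outs (type AD) will be" discarded. For 5% responders it adds that "individually predicted values for % weight change at week 56 will be used to classify each" subject as a responder or not.

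Protocol 17.3.3 has the same rule and continues: "This classification will then be analysed using a logistic regression model with treatment as the only factor". Neither document adds residual variation to the predictions or carries their uncertainty into the odds ratio. Multiple imputation with Rubin's formula is specified for the effectiveness estimand only (SAP 2.3.2.2).

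SAP 2.4.1 assesses the efficacy estimand for the confirmatory secondary endpoints, other than 4% responders at week 16, "using MMRM as described for the primary endpoints". These endpoints include the 10% and 15% responders. SAP 3.1 changes the treatment-pause rule in this section but leaves the classification step alone.

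**The concern.** Two separate errors follow from the rule.

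- **Biased rates.** Predictions for subjects without an on-treatment week-56 value cluster nearer their arm mean than their true values would. The share of predictions beyond a threshold is therefore not the share of subjects beyond it. The planning means of -9 and -4 lie on opposite sides of the -5 cut, so shrinkage raises the liraglutide rate, lowers the placebo rate and inflates the odds ratio. Both means lie above -10 and -15, so at those cuts the rates in both arms are pushed down.
- **Understated standard error.** The 0/1 result enters one logistic model as if it had been observed. All classifications within an arm depend on the same estimated parameters, and the model does not see that uncertainty.

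SAP section 2 says results will generally come with 95% confidence intervals and p-values. An odds ratio with these faults would be reported beside the primary result.

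The text also does not say whether subjects with an observed on-treatment week-56 value keep it, since the prediction rule covers every subject.

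**Working it through.** **Inputs.** From SAP 2.1: 141 per arm; completer means -9% and -4%; common SD 7; planning discontinuation 30%. In the earlier trial, "around 31% treatment discontinuations were observed in the placebo group, around 25% in the liraglutide 3.0 mg group".

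**Assumptions not in the documents.**
- Subjects who stop would have been like completers had they stayed on treatment.
- Subjects with an on-treatment week-56 value keep it.
- The correlation rho between the prediction and the true week-56 value is unknown, so a range is shown.

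**The plan's own figure.** True 5% responder rates are Phi((-5+9)/7) = 71.6% and Phi((-5+4)/7) = 44.3%. The 30% mixture in the liraglutide arm is 0.7 × 71.6% + 0.3 × 44.3% = 63.4%, against the stated 63%. The chi-square power for 63.4% vs 44.3% with 141 per arm is 90.0%, as stated (89.6% with the rounded 63% and 44%).

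**Analytic check.** With mean mu and threshold t (both as % change), the true responder rate is Phi((-t-mu)/7). A prediction has SD 7·rho, so the rate among predicted subjects is Phi((-t-mu)/(7·rho)). With a share d predicted, the arm rate is (1-d) × true + d × predicted.

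Example with t = 5, rho = 0.7, d = 0.30:
- Liraglutide predicted rate: Phi(4/4.9) = 79.3%. Arm rate: 0.7 × 71.6% + 0.3 × 79.3% = 73.9%.
- Placebo predicted rate: Phi(-1/4.9) = 41.9%. Arm rate: 0.7 × 44.3% + 0.3 × 41.9% = 43.6%.
- Odds ratio: (0.739/0.261)/(0.436/0.564) = 3.67. The true value is (0.716/0.284)/(0.443/0.557) = 3.17.

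Odds ratios under the planned method:

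| Endpoint, share predicted | True | rho 0.95 | 0.85 | 0.7 | 0.5 | 0.3 |
|---|---|---|---|---|---|---|
| 5%, 30% per arm | 3.17 | 3.23 | 3.37 | 3.67 | 4.34 | 5.61 |
| 5%, 25% liraglutide / 31% placebo | 3.17 | 3.22 | 3.34 | 3.60 | 4.16 | 5.23 |
| 10%, 30% per arm | 3.27 | 3.34 | 3.49 | 3.77 | 4.22 | 4.27 |
| 15%, 30% per arm | 3.95 | 4.06 | 4.26 | 4.42 | 4.14 | 3.77 |

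For 15% responders the arm rates are 18.4% vs 5.0% at rho 0.85 and 15.0% vs 4.1% at rho 0.5, against a true 19.6% vs 5.8%. Among the predicted subjects alone at rho 0.5, they are 4.3% vs 0.1%.

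**Standard error and coverage, 5% responders.** This simulation used 5,000 trials, 141 per arm, 30% missing completely at random and one on-treatment predictor. The planned method classified drop-outs from the within-arm fitted mean.

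| rho | 0.95 | 0.85 | 0.7 | 0.5 | 0.3 |
|---|---|---|---|---|---|
| Model SE of log OR too small by | 4% | 9% | 16% | 26% | 32% |
| Coverage of nominal 95% CI | 94% | 92% | 87% | 70% | 44% |

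Proper multiple imputation (50 imputations, Rubin's formula) in the same trials gave a median OR of 3.18 to 3.20 and coverage of 96% to 97%.

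**With more of the visit history.**
- Six visits, unstructured covariance, 30% drop-out spread evenly or early (600 trials per scenario), with visit correlation from 0.9 down to 0.6: planned OR 3.5 to 5.6, SE 5% to 26% too small, coverage 92% down to 44%. Multiple imputation from the same model gave OR 3.13 to 3.24 and coverage 96% to 98%.
- Twenty-two visits with drop-out spread over time: planned OR 3.4 to 4.3 and coverage 92% to 81%. Within-arm multiple imputation gave OR about 3.1 and coverage 96% to 98%.

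**The case against.** The best case on the other side has four parts.

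1. **Low stakes.** This is a secondary estimand outside the testing hierarchy. The primary responder analysis uses multiple imputation and has several sensitivity analyses. This stands and limits the priority. Those analyses target the effectiveness estimand, however, so they do not repair this one.
2. **The size rests on an unknown rho.** Weight is measured at every visit (Protocol 8.3.1), so predictions may be strong. At rho 0.85 to 0.95 the odds ratio moves only from 3.17 to between 3.23 and 3.37. That is small beside a 95% interval of about 1.9 to 5.2 (log-OR SE about 0.25). With both means at -6, a check gave null rejection rates of 5.6% (rho 0.95) and 7.0% (rho 0.85) against 5%. This also stands. Values of 0.3 and 0.5 for every drop-out are extremes, plausible only when most stop early. The 22-visit simulation with spread drop-out still gave 3.4 to 4.3, so the effect is not confined to those extremes.
3. **The figures quantify one reading.** They assume observed values are kept. Read literally, the text predicts every subject, which would make the distortion worse, so this does not weaken the point.
4. **The remedy may be over-parameterised.** Within-arm imputation on the full visit history, with about 99 completers per arm, could be unstable. The 22-visit check covered this, and the imputed odds ratio and coverage held up.

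**Conclusion.** The concern holds. As written, the rule does not estimate the proportion of responders under full adherence, and its standard error is too small. The existence of both faults is certain; their size depends on rho.

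For 5% and 10% responders the odds ratio is too high: slightly when on-treatment weights predict week 56 well, substantially when they do not. For 15% responders both rates are too low and the odds ratio can move either way. These results rest on the planning means and SD, on drop-outs resembling completers, and on observed week-56 values being kept.

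The primary effectiveness analysis, the testing hierarchy, the efficacy MMRM for % weight change and the sample size are not affected, and no confirmatory conclusion depends on this point. It should be corrected, but it is not critical.

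**What to change.** Replace the responder paragraph in SAP 2.3.3, and make the reference in SAP 2.4.1 follow it, so that the SAP:

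- states that observed on-treatment week-56 values are kept;
- multiply imputes the missing ones under MAR within each arm, from the same on-treatment data as the MMRM, with parameter and residual uncertainty (for example 100 draws); drawing from the fitted MMRM would make the same repair;
- derives 5%, 10% and 15% responders in each completed data set, fits the planned logistic model with treatment as the only factor, and pools the log odds ratios with Rubin's formula.

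Record the change in SAP 3.1 as a deviation from Protocol 17.3.3.

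The cost is SAP wording and one further imputation step; no new data are needed. The primary imputation cannot be reused, because it is placebo-based and "Body weight measurements at visits between baseline and week 56 are not used for this imputation approach". Rubin pooling and the logistic model are already planned.
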